Healthy adults with authorized access to Travis AFB will be offered the opportunity to participate in this study. After the consenting process is completed, subjects will be

For Protocol Office use only:

Protocol title: NATO Litter: Fluid Immersion System
(FIS) versus Traditional Mattress for Pressure Dispersion
FDG20160005H wAmd5

(investigator names redacted 23 Jan 20)

DGMC Human Research Protocol

scheduled for study participation. If time allows, the subject may be able to participate directly after completing the consent process. The subject will be assigned an identification (ID) number which will be annotated on the consent form and all of the data collection documents. The subject's name will only appear on the study consent form. All other study documents and data collection forms will only have the subject's ID number and no other personally identifiable information (PII). Subjects will be asked to wear a nonrestrictive single layer of garments for the study. They will be given a hospital gown to wear over the upper body. This will allow the study staff easy access to the subject's back for application of the transcutaneous oxygenation transducers. Females will not be required to remove their bra. Subjects will be asked their age and have their height and weight measured by a study team member. They will also be asked their litter and mattress preferences at the end of the study. The study portion should take approximately two hours to complete and can be broken into segments for multiple visits if necessary to accommodate a subjects schedule.

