5.4.4.2. A mattress pad is recommended to prevent skin breakdown."

After the subject is positioned comfortably on the litter, the pressure mapping will begin. The peak interface pressure (the highest average pressure (mm Hg) measured over each

For Protocol Office use only:

Protocol title: NATO Litter: Fluid Immersion System
(FIS) versus Traditional Mattress for Pressure Dispersion
FDG20160005H wAmd5

(investigator names redacted 23 Jan 20)

DGMC Human Research Protocol

body region) will be measured for the occiput, sacrum, bilateral scapula, buttocks and heel areas. The total body surface area exposed to skin interface pressure greater than 30mm Hg will also be measured in centimeters squared (cm²) for each body region. Measures of tissue perfusion using the tcpO₂ in mmHg will be measured for comparison to baseline data. This process will take approximately twenty minutes for each of the four iterations. An additional 30 minutes is required to change the litter and mattress configurations. After baseline data are captured and tcpO₂ measurements are taken with the subject supine on all four litter/mattress combinations, the session is complete. Data from subjects who do not complete all four litter/mattress combinations will be excluded from the analysis. An estimated 25% attrition rate is factored into this study to ensure that 43 completed data sets are obtained.

6.5. Risks/Benefits:

- There is a potential risk of injury from falling off the litter while attempting to mount or dismount. This risk will be minimized by having a member of the research staff present whenever a subject is on the litter. Staff will be available to assist participants on and off the litter. A step stool will also be available to assist participants in safely mounting and dismounting the litter.
- There is also a potential risk of skin reaction to the adhesive which will hold the transcutaneous oxygenation transducers in place. If a participant shows signs and/or symptoms of skin irritation from the adhesive (redness, itching, rash or hives), the adhesive will be removed and the participant will be encouraged to see their primary care provider if the signs and/or symptoms do not quickly resolve or becomes worse after the adhesive is removed. If the participant's initial reaction to the adhesive pads is severe (difficulty breathing, face/lips, throat swelling, loss of consciousness) the subject will be taken to the DGMC Emergency Department for treatment.

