6.6. Subject Population

Form Revised as of 14 Apr 14

G:\60MDG\SGSE\4. SGSE - Clinical Research\IRB Folder\IRB\Templates
and Forms\Master Protocol Office Forms (Do not delete)\Human

Page 11 of 24

For Protocol Office use only:

Protocol title: NATO Litter: Fluid Immersion System
(FIS) versus Traditional Mattress for Pressure Dispersion
FDG20160005H wAmd5

(investigator names redacted 23 Jan 20)

DGMC Human Research Protocol

Age Range: ≥ 18 y/o Children (≤ 18)

Sex: Male Female

Vulnerable Population: No Yes (explain)

Number of Subjects:

- Total Number of Subjects (nation-wide/study-wide): 43
- Number of Subjects Planned for DGMC: 43
- Number of Subjects Planned for (Specify Institution): N/A

Statistical tests will be 2-tailed with a significance level of 0.05. A 25% attrition rate is expected. A total of 53 subjects will be recruited in order to obtain 43 evaluable subjects with complete data sets.

Inclusion/Exclusion Criteria:

Inclusion:

- Adults over the age of 18 years with lawful access to Travis AFB.

Exclusion:

- Orthopedic or neurological conditions that prevent a subject from lying flat (supine) without any pillows for head, neck, or lumbar support
- Medical conditions (such as an uncontrollable tremor or twitch) that prevent a subject from staying still for the required periods of time (20 minute increments).
- Pregnancy
- Inability to ambulate unassisted, unstable gait (presenting increased fall risk)
- Extremity prosthetics (hand/arm or foot/leg)
- Height greater than 72 inches (6 feet) - exceeds length of the litter & mattress surfaces
- Body weight greater than 300 lbs

For Protocol Office use only:

Protocol title: NATO Litter: Fluid Immersion System
(FIS) versus Traditional Mattress for Pressure Dispersion
FDG20160005H wAmd5

(investigator names redacted 23 Jan 20)

DGMC Human Research Protocol

- Subjects who find it difficult, uncomfortable or impossible to remain still for the necessary study time durations (20 minute increments) on the relatively narrow litter surfaces will be removed from the study.
- Subject does not speak or understand the English language

Recruitment:

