1. **Fliers** – Will be posted throughout DGMC in approved/authorized locations such as Heart, Lung & Vascular, Family Medicine, Family Health, Internal Medicine and Flight Medicine clinics, cafeteria, elevators and other public areas. Advertisement posters/fliers will also be posted and briefed in other public buildings on Travis AFB in order to ensure recruitment of a sample representative of the active duty population. Research coordinators may also sit near advertisement posters in the clinic waiting room, common areas and cafeteria to answer any potential participant's questions.
2. **Pamphlets** – Will be placed in the waiting rooms of primary care clinics, base gym, Base Exchange (BX), hospital cafeteria and Grant Central Station.
3. **E-mail/Newspaper** – The research team may elect to advertise the study via e-mail sent out by Wing public affairs office. The research team may also elect to advertise via Air Force newspaper publications or other military newspapers at surrounding bases.
4. **Marquee** – Base and MDG

Consent:

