Underweight = <18.5

Normal weight = 18.5–24.9

Overweight = 25–29.9

Obesity = BMI of 30 or greater

Ideal = 18.5-24.9

High = 25 or greater

This is a cross-factor design that will use a Repeated Measures Analysis of Variance (ANOVA) model to examine the effects of within and between factors. Mean change in tcpO₂ (mmHg), LDP pressure units, surface area (cm²) will be computed. All analyses will be done using STATA v 13.0 (College Station, TX).

Source of Research Material per Participant:

| Source of Research Material per Participant | Standard Care | Research Driven |
|--|---------------|-----------------|
| Demographic Data | 0 | 1 |
| Age in years (89+ for anyone over 89 years of age) | 0 | 1 |
| Gender – Male or Female | 0 | 1 |
| Body Mass Index (BMI) | 0 | 1 |
| Height (centimeters/inches) | 0 | 1 |
| Weight (pounds/kilograms) | 0 | 1 |
| Pressure Mapping (mmHg) - NATO Litter (WELP) | 0 | 1 |
| Transcutaneous Oxygenation (TcPO ₂) mmHg | 0 | 4 |
| Pressure Mapping (mmHg) - NATO Litter (FIS) | 0 | 1 |
| Transcutaneous Oxygenation (TcPO ₂) mmHg | 0 | 4 |
| Pressure Mapping (mmHg) – Raven Litter (WELP) | 0 | 1 |
| Transcutaneous Oxygenation (TcPO ₂) mmHg | 0 | 4 |
| Pressure Mapping (mmHg) - Raven Litter (FIS) | 0 | 1 |
| Transcutaneous Oxygenation (TcPO ₂) mmHg | 0 | 4 |
| | | |
| | | |
| | | |
| | | |

7. Conflict of Interest

None

8. Investigation Schedule

Estimated Timeline: IRB approval estimated for May 2016. PI PCS'd and alternate deployed, therefore, anticipated protocol start date Jan 2018 protocol start (need additional equipment, supplies, also requesting additional funding).

| | Jan 2018 Y2Q2 | Y2 Q3 | Y2 Q3 | Y2 Q4 | Y3 Q1 | Y3 Q2 | Y3 Q3 | Y3 Q4 |
|-------------|------------------|-------|-------|-------|-------|-------|-------|-------|
| Recruitment | X | X | X | X | | | | |
| Enrollment | X | X | X | X | X | X | | |

For Protocol Office use only:

Protocol title: NATO Litter: Fluid Immersion System
(FIS) versus Traditional Mattress for Pressure Dispersion
FDG20160005H wAmd5

(investigator names redacted 23 Jan 20)

DGMC Human Research Protocol

| | | | | | | | | |
|----------------------|---|---|---|---|---|---|---|---|
| Data Collection | X | X | X | X | X | X | | |
| Statistical Analysis | | | | | | X | X | |
| Publications/Reports | | | | | | X | X | X |

9. Use of Investigational Drug(s) No Yes

10. Use of Investigational Device(s) No Yes

11. Support Required

CIF Support:

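### The eligibility criteria do not enforce the healthy, active-duty-like sample that the protocol describes, and the sex comparisons in Hypotheses 2 and 3 have no age adjustment

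*Combined protocol and SAP*

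**What the plan says.** The combined protocol describes its subjects in three ways.

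- **Section 6.4, Research Design and Methods:** "Healthy adults with authorized access to Travis AFB will be offered the opportunity to participate in this study".
- **Section 6.6, Recruitment:** posters also go to other public buildings on the base "in order to ensure recruitment of a sample representative of the active duty population".
- **Section 6.6, Inclusion/Exclusion Criteria:** the sole inclusion criterion is "Adults over the age of 18 years with lawful access to Travis AFB".

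Two exclusions mention medical conditions, and both depend on what the subject can do: "Orthopedic or neurological conditions that prevent a subject from lying flat (supine) without any pillows for head, neck, or lumbar support" and "Medical conditions (such as an uncontrollable tremor or twitch) that prevent a subject from staying still for the required periods of time". The rest are pregnancy, inability to walk unaided or an unstable gait, limb prosthetics, height over 72 inches, weight over 300 lb, inability to remain still on the narrow litter, and not speaking or understanding English. Age has no ceiling, and the data table in Section 6.8 has a row headed "Age in years (89+ for anyone over 89 years of age").

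Section 6.3 states Hypotheses 2 and 3 as differences in pressure distribution between men and women at a given BMI level, on the WELP and on the FIS. Section 6.8 stratifies sampling by sex and BMI class, collects age, race, sex, height and weight, and names a repeated-measures ANOVA with within and between factors. It names no covariate.

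**The concern.** The list that staff apply at enrolment does not enforce either description of the population. An older volunteer with a stable chronic illness who can walk, lie flat and keep still is eligible, although the methods say that healthy adults are being studied. The report could then not properly call its sample healthy, or like active duty personnel.

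The analytic stake is narrower. Hypotheses 2 and 3 are non-randomized comparisons between people. Sex and BMI class are fixed by the sampling scheme, but age is not. If the men who volunteer tend to be older than the women, or the reverse, and age is related to interface pressure, part of an age difference would be reported as a sex difference.

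**Working it through.** **1. The statements side by side.**

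| Attribute | Section 6.4 | Section 6.6, Recruitment | Section 6.6, criteria |
|---|---|---|---|
| Health | Healthy | Not stated | No criterion beyond the functional exclusions and pregnancy |
| Age | Adult | As in active duty | Over 18, no ceiling |
| Service status | Base access | Like active duty | Base access only |

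No criterion enforces health or resemblance to active duty personnel.

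**2. Which hypotheses are exposed.** Every subject is measured on all four litter and mattress combinations, in an order randomized per participant (Section 6.4). A personal characteristic that shifts all four readings equally cancels from WELP against FIS and from NATO against Raven. Hypotheses 1, 4 and 5 are therefore largely protected. Hypotheses 2 and 3 compare different people, so nothing cancels.

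**3. Cell size.** Sections 6.6 and 6.8 give 43 evaluable subjects. No allocation to cells is stated, so equal cells are assumed: 43 / 4 = 10.75 per sex-by-BMI cell and 43 / 2 = 21.5 per sex. N = 43 itself cannot be reproduced, because no effect size or SD is given; it is taken as stated.

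**4. Chance imbalance in age.** The documents give no age SD; 15 to 20 years is assumed. SE of the difference in mean age = SD × √(1/n₁ + 1/n₂).

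- All men against all women, 21 v 22: 15 × 0.305 = 4.6 years; 20 × 0.305 = 6.1 years.
- Within one BMI level, 10.75 v 10.75: 15 × 0.431 = 6.5 years; 20 × 0.431 = 8.6 years.

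Gaps of this order are ordinary sampling variation. The test's standard error already contains them, so they cost precision and do not inflate the error rate.

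**5. Systematic imbalance.** Suppose that a factor (older age, for example) shifts the outcome by 0.5 to 1.0 SD and that its prevalence differs by 10 to 40 percentage points between the sexes. These values are assumptions. Bias b = prevalence difference × shift, from 0.10 × 0.5 = 0.05 SD to 0.40 × 1.0 = 0.40 SD. With no true sex effect, the chance of rejection is Φ(b√(n/2) − 1.96) + Φ(−b√(n/2) − 1.96), with n per group.

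| Bias b (SD) | 21.5 v 21.5 | 10.75 v 10.75 |
|---|---|---|
| 0 | 0.050 | 0.050 |
| 0.05 | 0.053 | 0.052 |
| 0.20 | 0.101 | 0.075 |
| 0.40 | 0.259 | 0.153 |

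For scale, the difference detectable with 80% power is (1.96 + 0.84) × √(2/n): 0.85 SD for 21.5 v 21.5 and 1.21 SD for 10.75 v 10.75.

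**6. The same factor, equally common in both sexes.** There is no bias. The SD rises to √(1 + p(1 − p) × shift²). For prevalence p of 10% to 50% and shifts of 0.5 to 1.0 SD, power at a difference of 0.85 SD (21.5 v 21.5) falls from 0.80 to between 0.79 and 0.71.

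**The case against.** Much of the case on the other side stands.

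- **The outcome is mechanical.** Section 6.3 defines pressure redistribution as PPI and TSA and lists tcpO₂ separately under tissue perfusion. Arterial or lung disease might affect skin oxygen, but the documents give no reason why it would change interface pressure. The exposure in Hypotheses 2 and 3 is therefore mainly to age, and the documents do not give the size of an age effect on PPI or TSA either.
- **tcpO₂ is analysed as change.** A reader might infer that absolute readings from healthy and diseased skin will be tested against 80, 44 or 30 mmHg. Those values are background. Section 6.4 compares readings with the subject's own baseline, and Section 6.8 computes mean change.
- **The criteria do not admit every disease.** A reader might infer this from the single inclusion line, but conditions that prevent lying flat, keeping still or walking safely do exclude.
- **The clinic fliers prove little.** Section 6.6 lists "approved/authorized locations such as Heart, Lung & Vascular, Family Medicine, Family Health, Internal Medicine and Flight Medicine clinics" along with the cafeteria, elevators, gym and Base Exchange. A flier in one specialist clinic does not show that ill people will be enrolled. Nor does the row for ages over 89, which only groups the highest ages, show an intention to enrol them.
- **The active duty phrase is a recruitment aim,** not an eligibility rule. It still describes a sample that the criteria do not secure.
- **The adhesive risk is not a contradiction.** Section 6.5 says what happens "If the participant's initial reaction to the adhesive pads is severe (difficulty breathing, face/lips, throat swelling, loss of consciousness"). A risk statement without a matching exclusion is not inconsistent.

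These points narrow the concern. They do not make the Section 6.4 description agree with the Section 6.6 criteria, or put age into the model.

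**Conclusion.** The mismatch is real and can be read directly from the text: the criteria do not deliver the population that Sections 6.4 and 6.6 describe. Its effect on the major aim and on Hypotheses 1, 4 and 5 is small, because those contrasts are within subject; what is affected there is how the sample may be described.

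For Hypotheses 2 and 3 the problem is a risk of bias. A reader might infer that confounding is established. It is not: it needs a systematic age difference between the sexes and a relation of age to PPI or TSA, and the documents show neither. If both held at the assumed sizes, the true error of a nominal 0.05 test would range from scarcely changed (0.052 or 0.053) to 0.15 within one BMI level or 0.26 for all men against all women. Chance age gaps alone add only variance. These figures rest on equal cells, a normal approximation and assumed shifts and imbalances. The change is worth making because it is cheap, and because otherwise any systematic age difference stays in the sex comparison.

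**What to change.** 1. **Make Sections 6.4 and 6.6 agree.** Either add a healthy-by-self-report inclusion criterion to Section 6.6, or delete the word healthy from Section 6.4 and describe the sample as enrolled. In either case, bring the active duty wording under Recruitment into line. If the first option is taken, record only eligible or not eligible, so that the statement in Section 6.7 that health information is not accessed or recorded still holds.
2. **Prespecify age as a covariate** in the Hypothesis 2 and 3 comparisons in Section 6.8. Age is already collected.

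**Cost.** A short amendment and, under the first option, a brief screening question and a few volunteers turned away. The covariate uses one between-subject degree of freedom: 43 − 4 = 39 without age, 38 with it, assuming a linear age effect common to all cells. Under the second option, comorbidity stays unrecorded and cannot be adjusted for, and the report should say so.
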